3.03.2017

The Effect of Vest Type Dynamic Elastomeric Fabric Orthosis (DEFO) on Sitting Balance and Gross Manual Dexterity in Children With Bilateral Cerebral Palsy: A Feasibility and Randomized, Single-blinded, Pilot Study (NCT03191552)

(Unique Protocol ID:09.2013.0351)

STATISTICAL PLAN

IBM SPSS Statistics for Windows, Version 20,0 (Armonk, NY, USA) will be used to perform all of the analysis. Statistical significance is accepted as $p < 0.05$. Descriptive statistics will be used to determine mean \pm SD of data. Chi-square and t-tests will be used to compare demographic findings. The histogram and normality plots and Shapiro-Wilk normality test were used for data distribution analysis. Between group analysis will be performed using ANOVA if data followed normal distribution. But if not Kruskal-Wallis test will be performed. Mann-Whitney U test was performed to test the significance of pairwise differences using Bonferroni correction (post-hoc test) to adjust for multiple comparisons. For Bonferroni correction, a p value of less than 0.017 ($0.05/3$) was determined as the level of statistical significance

Depending on the distribution analysis, Wilcoxon and dependent t-test will be utilized to detect within group analyzes. To assume changes over time with treatment Friedman and repeated measures analysis of variance will be conducted.

Mann Whitney u and independent sample t-tests will be applied to compare SPIO 2 hours and 6 hours group. To compare groups in pairs in terms of parent satisfaction questionnaire results chi square test will be done.

To evaluate feasibility, recruitment and retention rates will be calculated and percentages will be reported.

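### The only three-group post-hoc test is Mann-Whitney at 0.017: the ANOVA branch has none of its own, and after a significant omnibus test the Bonferroni step is unnecessary and costs roughly 9 to 19 points of power

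*SAP*

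**What the plan says.** All of this is in the SAP, under STATISTICAL PLAN. The general significance level is 0.05.

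- **Omnibus test.** "Between group analysis will be performed using ANOVA if data followed normal distribution". For other data, "But if not Kruskal-Wallis test will be performed".
- **Pairs after the omnibus test.** The next sentence reads "Mann-Whitney U test was performed to test the significance of pairwise differences using Bonferroni correction (post-hoc test) to adjust for multiple comparisons". The threshold is "a p value of less than 0.017", shown as 0.05/3.
- **The two garment arms.** A later paragraph adds "Mann Whitney u and independent sample t-tests will be applied to compare SPIO 2 hours and 6 hours group". It states no threshold and does not say which outcomes it covers.
- **Parent survey.** "To compare groups in pairs in terms of parent satisfaction questionnaire results chi square test will be done". No correction is stated.

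No sentence says that pairs are tested only when the omnibus test is significant, and no parametric post-hoc test is named. The protocol (Study design) has exactly three arms: SPIO 2 hours, SPIO 6 hours and control.

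**The concern.** There are two linked gaps.

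First, the plan branches on normality for the omnibus test but names only one post-hoc test, a rank test. If that test also serves the ANOVA branch, a comparison of means is followed by a test of a different hypothesis. If it does not, the ANOVA branch has no pairwise procedure, and one would be chosen after the data are seen.

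Second, if the omnibus test acts as a gate at 0.05, a Bonferroni threshold on top corrects again for a multiplicity that the gate already handles when there are three groups. The trial plans 8 children per arm, so the power given up is a real loss. The main question, whether either wear time beats control on the Sitting Assessment Scale (SAS), is answered by these pairwise tests.

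**Working it through.** **Inputs.** Protocol, Sample size: means 16.47 (SD 1.96) and 13.20 (SD 3.32), 8 per group, 80% power, 5% type I error. SAP: 0.05 overall and 0.017 for pairs. The documents give no mean or SD for a third group. It is assumed equal to the low group, midway, or equal to the high group, with either a common SD or the unequal planning SDs. Tests are taken as two-sided, which the SAP does not state.

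**The plan's own figure.** Difference = 16.47 − 13.20 = 3.27. Common SD = √[(1.96² + 3.32²)/2] = √7.432 = 2.726. Standardised difference = 3.27/2.726 = 1.20. Normal approximation: n = 2(1.960 + 0.842)²/1.20² ≈ 11 per group (12 by exact t). One-sided testing gives 9. Exactly 8 appears if the 1-unit difference is added (4.27, two-sided, noncentral t, power 0.829). So 8 is reached, or nearly reached, only under variants the protocol does not state. Here it serves only to fix n.

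**Cost of the threshold alone.** With n = 8, the noncentrality is 1.20 × √(8/2) = 2.40.
- At 0.05: Φ(2.40 − 1.96) ≈ 0.67.
- At 0.05/3: Φ(2.40 − 2.39) ≈ 0.50; about 15 per group would be needed for 80%.

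The exact Mann-Whitney test is coarse at 8 versus 8. U ≤ 9 gives p = 0.0148 and U ≤ 10 gives p = 0.0207, so without ties the level actually used below 0.017 is 0.0148.

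**Why three groups need no further correction after a gate.** There are three pairwise null hypotheses. If any two are true, all three group means are equal. The true state is therefore one of two: all three nulls hold, and a false claim first requires the omnibus test to reject, which happens at most 5% of the time; or exactly one null holds, and a single test at 0.05 limits its error to 5%. This is closed testing, and it works as long as each test holds its own level.

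**Family error, simulated** (8 per arm, normal data):

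| Procedure | Family error |
|---|---|
| As written (gate, then Mann-Whitney at 0.017) | 2.9-3.6% |
| Kruskal-Wallis, then Mann-Whitney at 0.05 | 4.7-5.1% |
| Welch ANOVA, then Welch pairs at 0.05 | 4.8-5.0% |

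**Power for one 16.47 versus 13.20 pair, simulated:**

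| Setting | As written | Kruskal-Wallis, Mann-Whitney 0.05 | Welch, Welch pairs 0.05 |
|---|---|---|---|
| Third arm high, common SD 2.73 | 36% | 50% | 50% |
| Third arm high, SDs 1.96/3.32 | 37% | 51-52% | 48% |
| Range over all third-arm settings | 34-38% | 44-52% | 45-53% |

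The smallest gain is about 44 − 35 = 9 points (third arm midway). The largest is about 53 − 34 = 19 points (third arm low, unequal SDs, Welch path).

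**Where the loss comes from.** Mann-Whitney at 0.0167 with no gate has 36.4-37.7% power. With an ANOVA gate it has 34.2-37.0%. Setting by setting, the gate costs only 0.3 to 3.5 points, so nearly all of the loss comes from the 0.017 threshold.

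**The case against.** The strongest reply is that the plan may contain no double correction. The Mann-Whitney sentence comes directly after the Kruskal-Wallis sentence and may belong to that branch alone. The gate is nowhere written: without one, Bonferroni is the only multiplicity control and is needed. Both points stand as readings. On the first, the ANOVA branch simply has no pairwise test. On the second, 0.017 may be dropped only if the gate is written in, and the net gain is smaller by the 0.3 to 3.5 points that the gate costs.

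A reader might infer three stronger things that the documents do not support.

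- **Every pairwise comparison uses Mann-Whitney at 0.017.** The SAP itself allows t-tests for the two SPIO arms and plans chi-square tests for the survey.
- **The loss reaches about 25 points.** That figure compares the plan with ANOVA followed by pooled-error contrasts under unequal SDs. In that situation pooled contrasts can reject a true null pair about 8% of the time, so this is not power that a valid procedure would keep.
- **The 2 h versus 6 h contrast definitely has two thresholds.** It may not. The protocol measures an immediate effect with the garment on (Outcome measures) and uses the full survey only to compare the SPIO groups (Parent Satisfaction Survey). The separate test may be meant for those outcomes, where a three-group correction has no place. The SAP leaves this open.

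It is also fair to say that this is a feasibility pilot with several outcomes and time points and no stated correction across them. Preferring a conservative pairwise rule is a legitimate choice if made knowingly.

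**Conclusion.** The point holds as a gap in specification and an avoidable loss of power. It is not an error that threatens validity: the current rule keeps family error below 5%. The missing post-hoc test for the ANOVA branch follows from the text alone. The unnecessary Bonferroni step depends on reading post-hoc as conditional on a significant omnibus test.

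The gain of roughly 9 to 19 points rests on 8 children per arm, the protocol's planning means and SDs, normal continuous data and an assumed third arm. SAS scores are whole numbers from 5 to 20, so ties will occur and the exact level of 0.0148 will not apply strictly. With simulated scores rounded to whole points and the third arm high (either SD assumption) or low (unequal SDs), power was about 31-33% as written. It was 46-54% for an ANOVA gate followed by Mann-Whitney at 0.05, so the direction does not change.

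**What to change.** Amend the SAP to say, for each outcome and time point measured in all three arms:

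1. The omnibus test at 0.05 is the gate. Pairs are tested only if it is significant.
2. The pairwise test matches the gate: Welch pairs after Welch ANOVA, Mann-Whitney after Kruskal-Wallis. Pooled-error contrasts are not used when SDs differ.
3. The three pairs are tested at 0.05, and the 0.017 rule is removed.
4. SPIO 2 h versus 6 h is tested only inside this family. The separate two-arm test is limited to outcomes measured only in the SPIO arms (immediate effect, full parent survey), and those outcomes are listed.
5. Each pairwise difference is reported with a 95% confidence interval.

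The cost is SAP wording only, with no new data or visits. There are two downsides. No pair can be declared when the omnibus test is not significant, and unadjusted 95% intervals may not always agree with the gated decisions, which the report should say. Because the change relaxes a threshold, it should be dated before between-group results are seen.

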## Study design

The study was designed as prospective, single-blinded, randomized, controlled trial. Children with CP were randomized to either of three groups: SPIO 2 hours, SPIO 6 hours and control group (EKS) which the assessors were blinded to (EG, TO). To ensure group concealment, randomization was done using sealed opaque envelopes which were sequencly numbered in

advance, including the information about which group the child would have been allocated to. The physiotherapist opened the envelopes and started the interventions according to group allocation.

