# Sample size

It was found out that 8 individuals for each group must had been recruited to have 80% power with 5% type 1 error level to detect a minimum clinically significant difference of 1 units of Sitting Assessment Scale score, when the average expected value in the first group was 16.47, with a standard deviation of 1.96 and the average expected value in the second group was 13.20, with a standard deviation of 3.32 based on the previous research conducted by Şimşek et al evaluating the effects of kinesiology taping on trunk control .

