# Intervention

All children were hospitalized for 2 weeks and received conventional exercise therapy including range of motion, strengthening, trunk control and strengthening exercises and exercises to improve fine and gross motor skills during hospital inpatient stay throughout 2 weeks 2 hours a day (SG). Control group received conventional exercise therapy only. SPIO 2 hours group received conventional exercise therapy with the garment on for 2 hours. SPIO 6 hours group wore the SPIO 4 hours more in addition to 2 hours during therapy. After the treatment for two weeks, during the follow-up period SPIO groups continued wearing the orthosis at home and all the children continued their regular therapies for one hour a day, two days a week. After hospitalization, wear time of garment during follow-up was checked by weekly phone calls. No other changes in physiotherapy or orthotic management or no addition of a new treatment method were permitted during follow-up.

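### The sample size claims 80% power at a 5% level, but the SAP tests each pair of groups at 0.017, where power on the protocol's own figures is about 40%

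*SAP*

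**What the plan says.** - **Protocol, Sample size:** "8 individuals for each group must had been recruited to have 80% power with 5% type 1 error level". The expected values come from an earlier kinesiology taping study: 16.47 (SD 1.96) in the first group, and "the average expected value in the second group was 13.20, with a standard deviation of 3.32". The section also names a target difference of 1 point on the Sitting Assessment Scale (SAS). It mentions neither sidedness nor any adjustment for three groups.
- **Protocol, Study design and Intervention:** there are three randomised groups, SPIO 2 hours, SPIO 6 hours and control. On the last: "Control group received conventional exercise therapy only".
- **Protocol, Outcome measures:** SAS is the primary outcome measure, and feasibility is also a primary interest.
- **SAP:** ANOVA or Kruskal-Wallis is used across the three groups. For the pairs: "Mann-Whitney U test was performed to test the significance of pairwise differences using Bonferroni correction (post-hoc test) to adjust for multiple comparisons". The corrected level is 0.05/3, given as 0.017. A separate sentence compares the two SPIO groups and gives no adjusted level.

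**The concern.** The sizing and the analysis use different error levels, and neither document says so. The sizing treats the trial as one comparison of two groups of 8 at 5%. The analysis makes three such comparisons and judges each at one third of that level. Anyone relying on the stated 80% would expect a garment effect of the planned size to be detected in four trials out of five for a given pair. If the true figure is about two in five, a non-significant pair says little about whether the garment works, and the 80% claim would lead readers to over-interpret it. The third pair, SPIO 2 hours against 6 hours, compares two active arms, and nothing in the sizing says what difference is expected there.

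**Working it through.** **Inputs.** From Sample size: means 16.47 and 13.20, SDs 1.96 and 3.32, 8 per group, 80% power, 5% level. From the SAP: pairwise level 0.017. Assumed, because not stated: two-sided tests, normal scores, one visit, no dropout.

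**Basic quantities.**
- Difference: 16.47 − 13.20 = 3.27.
- Root-mean-square SD: √((1.96² + 3.32²)/2) = √(14.864/2) = 2.726, so the standardised difference is 3.27/2.726 = 1.20.
- Standard error with 8 against 8: √(14.864/8) = 1.363. Difference over standard error: 3.27/1.363 = 2.399.

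**Step 1: the plan's own figure.** By normal approximation, n per group = 2(z₁ + z₂)² × 2.726²/3.27², where z₁ is the critical value and z₂ = 0.842 for 80% power.
- Two-sided 5%: 2 × (1.960 + 0.842)² × 7.432/10.693 = 10.9, so 11 (12 by t-test).
- One-sided 5%: 2 × (1.645 + 0.842)² × 7.432/10.693 = 8.6, so 9 (10 by t-test).

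Eight is close only under a one-sided reading that the protocol does not state. Even then, power with 8 per group is 77.5% (normal) or 73.8% (t), not 80%. If the 1-point difference were the target, about 117 per group (two-sided) would be needed. The 3.27 used here is the reading more favourable to the plan.

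**Step 2: effect of the level.** By normal approximation, power = Φ(2.399 − z₁).
- At 0.05: Φ(2.399 − 1.960) = Φ(0.439) = 67.0%.
- At 0.017: Φ(2.399 − 2.387) = Φ(0.012) = 50.5%.

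The t-test figures use the noncentral t distribution with 14 degrees of freedom and noncentrality 2.399. The Mann-Whitney figures come from simulating the exact test with the two separate SDs (40,000 runs).

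| Method, 8 against 8, two-sided | 0.05 | 0.017 | Loss (points) |
|---|---|---|---|
| Normal approximation | 67.0% | 50.5% | 17 |
| t-test | 60.7% | 40.9% | 20 |
| Exact Mann-Whitney (the SAP's pairwise test) | 57.9% | 37.2% | 21 |

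One-sided, the fall is from 77.5% to 61.0% (normal) or from 73.8% to 53.4% (t).

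**Step 3: if 80% at 5% is taken as given.** The two-sided normal approximation becomes Φ(1.960 + 0.842 − 2.394) = Φ(0.408) = 66% at 0.05/3; the t-test gives 62%. The loss is then 14 to 18 points, so the mismatch does not depend on the sizing arithmetic in Step 1.

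**Step 4: what 80% per pair at 0.05/3 would need.** 2 × (2.394 + 0.842)² × 7.432/10.693 = 14.6, so 15 per group (17 by t-test), against 8 planned.

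**The case against.** **Garment against no garment is not missing.** The SAP's title asks for the effect of the vest, and no test combines the two SPIO arms. A reader might infer that the SAP never compares children with the garment against children without it. The documents do not support that. The control group has exercise only, so two of the SAP's three pairs are exactly that comparison. The sizing was also for 8 against 8, which matches those pairs. A 16 against 8 contrast appears nowhere in the documents, so the SAP has not dropped something that was sized.

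**A combined contrast is not clearly better.** Simulation compared two routes to a significant SPIO against control result. The planned route was a significant ANOVA, then Mann-Whitney at 0.017 for either SPIO arm; the ANOVA gate is an assumption. The combined route was a Welch t-test of 16 against 8 at 0.05. The 6-hour effect was 3.27 throughout. Figures are good to about 2 points.

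| 2-hour effect as share of 6-hour effect | Common SD 2.73: planned / combined | SD 1.96 in SPIO arms, 3.32 in control: planned / combined |
|---|---|---|
| 100% | 50% / 73% | 48% / 64% |
| 50% | 36% / 48% | 38% / 41% |
| 25% | 35% / 34% | 36% / 29% |
| 0% | 36% / 21% | 39% / 20% |

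Combining helps when the two wear times act alike and hurts when the 2-hour effect is about a quarter of the 6-hour effect or less. The documents give no basis for choosing between these cases, and separating wear times is a legitimate design choice.

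**The 0.017 level could have been avoided.** With exactly three groups, testing pairs at 0.05 only after a significant omnibus test holds the family-wise error, provided the tests keep their nominal levels. That is correct, but the SAP does not state such a rule; it fixes 0.017.

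**This is a pilot with feasibility among its primary aims.** That stands and lowers the weight of the point. It does not remove it, because the protocol makes SAS the primary measure and claims 80% power for it.

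**Conclusion.** The point holds as a mismatch of error levels. The 80% at 5% in Sample size does not describe the pairwise tests in the SAP. On the protocol's own means and SDs, each SPIO against control pair has about 41% power by t-test and 37% by the SAP's Mann-Whitney test. Moving from 0.05 to 0.017 accounts for 17 to 21 points. The rest of the shortfall from 80% is already there at two-sided 5%, where power is 58% to 67%, so the loss should not be read as a fall from a true 80% to 60%.

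This rests on two-sided tests, a true difference of 3.27, normal scores, and no dropout. It also reads the protocol's first and second groups as a treated and an untreated group. The protocol does not label them, but the figures apply to any pair of 8 with those values. The documents do not support the further inferences that garment against no garment goes untested or that a combined contrast must be primary.

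**What to change.** In the protocol's Sample size section:

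1. State that 8 per group refers to one SPIO arm against control on SAS.
2. Name the error level actually used for that comparison (0.017) and whether it is two-sided.
3. Restate the power at that level as about 40% (37% by Mann-Whitney, 41% by t-test, for a 3.27-point difference).
4. Say that SPIO 2 hours against 6 hours was not sized and is exploratory, and label the SAP's separate comparison of those groups in the same way.

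Optionally, add to the SAP a supportive estimate of both SPIO arms together (n = 16) against control (n = 8). Use a Welch t-test: with the protocol's unequal SDs, simulation puts the false-positive rate of the equal-variance t-test at about 9.5%, against 5.3% for Welch. Keep the existing pairs, since the combined estimate is diluted if the wear times differ in effect.

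The cost is a few sentences and, if wanted, one extra contrast. No more children, visits or data are needed. The price is an openly lower power figure.

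### The SAP's only stated analyses of change over time are within-group or have no stated group-by-time term, and within a SPIO arm they cannot separate the garment from the inpatient therapy given to every arm; they should rank below a between-arm comparison of change from BT

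*SAP*

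**What the plan says.** **Treatment (Protocol, Intervention).** The inpatient programme is common to all arms: "All children were hospitalized for 2 weeks and received conventional exercise therapy", at 2 hours a day. Controls have this therapy alone. The SPIO 2 h arm has it with the garment on, and the SPIO 6 h arm wears the garment for 4 hours more. After the two weeks the SPIO arms keep wearing the garment at home, and "all the children continued their regular therapies for one hour a day, two days a week".

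**Visits (Protocol, Outcome measures).** Assessments are at BT, at the end of treatment (PT), and 1 and 3 months later (1 MPT, 3 MPT). SAS and BBT are also tested once with the garment just put on.

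**Analysis (SAP, Statistical Plan).**
- Between groups: ANOVA or Kruskal-Wallis over the three arms, pairwise Mann-Whitney tests at 0.017, and a separate comparison of SPIO 2 h with SPIO 6 h.
- Within groups: "Wilcoxon and dependent t-test will be utilized to detect within group analyzes", the choice depending on the distribution.
- Over time: "To assume changes over time with treatment Friedman and repeated measures analysis of variance will be conducted".
- The general significance level is 0.05. The SAP does not say whether the between-group tests use raw scores or change from BT, whether the repeated measures ANOVA has a group factor, or which test decides the question about the garment.

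**The concern.** The title asks about the effect of the orthosis. Within a SPIO arm, the change from BT to PT is the sum of any garment effect, two weeks of daily therapy, and whatever else changes in children aged 3 to 7. Change to the later visits also carries the fall in therapy after the inpatient stay and further development. No test confined to one arm can separate these parts.

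The comparison with control can, because control has the same therapy. But the SAP lists within-group and between-group tests side by side, without ranking them, and ties change over time only to the within-group tests and an ANOVA of unstated form. With 8 children per arm, a shared therapy effect can easily reach p < 0.05 in one arm and miss it in another by chance. If a SPIO arm is significant and control is not, the report could present this as support for the garment, and nothing in the SAP prevents that.

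**Working it through.** **1. The plan's own figure.** Protocol, Sample size, states "8 individuals for each group must had been recruited". Its inputs are a mean SAS of 16.47 (SD 1.96) in one group and 13.20 (SD 3.32) in the other. The difference is 16.47 − 13.20 = 3.27. The pooled SD is √((1.96² + 3.32²)/2) = 2.726. With n = 2(z_α + z_β)²(SD/difference)² and (2.726/3.27)² = 0.695:
- one-sided 5%, 80% power: 2 × (1.645 + 0.842)² × 0.695 = 8.6, so 9 per group, close to the stated 8;
- two-sided 5%: 2 × (1.960 + 0.842)² × 0.695 = 10.9, so 11.

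The sample size is a separate matter. I take 8 per arm as planned and use 2.726 as the SD below.

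**2. Therapy dose.** Two hours a day is 10 to 14 hours a week, assuming 5 or 7 days a week (the Protocol does not say). Afterwards it is 2 hours a week, so the fall is 5- to 7-fold in every arm. Therapy before admission is not stated.

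**3. Chance of a misleading pattern.** Assume no garment effect, the same true standardised change d (mean change divided by SD of change) in each arm, independent arms, 8 children per arm, and a two-sided paired t-test at 0.05 (df 7, critical value 2.365, noncentrality d√8). Let p be the power in one arm. The chance that at least one of the two SPIO arms is significant and control is not is

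(1 − p) × [1 − (1 − p)²].

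| d (assumed) | p | Chance of the pattern |
|---|---|---|
| 0.2 | 0.078 | 0.139 |
| 0.5 | 0.232 | 0.315 |
| 0.8 | 0.496 | 0.376 |
| 1.0 | 0.681 | 0.287 |
| 1.2 | 0.828 | 0.167 |
| 1.5 | 0.951 | 0.049 |

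For d = 0.8: 0.504 × (1 − 0.504²) = 0.376. The formula peaks at 0.385, when 1 − p = 1/√3.

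**4. Are these values of d plausible in SAS units?** The documents give no SD of change. With SD 2.726 and within-child correlation ρ (assumed), d = gain / (2.726 × √(2(1 − ρ))). A shared gain of 1 unit, the Protocol's minimum clinically significant difference, gives d = 0.37, 0.47 and 0.82 at ρ = 0.5, 0.7 and 0.9. A gain of 2 units gives 0.73, 0.95 and 1.64.

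**5. The same question for repeated measures ANOVA.** Simulation with 20,000 trials per setting: three arms of 8, four visits, SD 2.726, the same gain in all arms at every visit after BT, no garment effect, normal scores, no dropout. The within-arm ANOVA is run in each arm at 0.05.

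| Gain (SAS units) | ρ | One SPIO arm significant | Either SPIO arm significant, control not | Between-arm ANOVA on BT-to-PT change |
|---|---|---|---|---|
| 0 | 0.5 / 0.7 / 0.9 | 5% / 5% / 5% | 9% / 10% / 9% | 4.9% / 5.1% / 5.0% |
| 1 | 0.5 / 0.7 / 0.9 | 14% / 21% / 57% | 23% / 30% / 35% | 5.2% / 4.9% / 5.0% |
| 2 | 0.5 / 0.7 / 0.9 | 47% / 71% / 99.5% | 38% / 27% / 0.4% | 4.8% / 5.1% / 5.2% |

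Friedman in one SPIO arm is significant in 11% to 42% of trials at a gain of 1 unit and in 34% to 96% at 2 units. The between-arm ANOVA stays near 5% throughout, on change or on raw PT scores.

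**The case against.** The strongest reply is that the plan already contains the right comparison. Control has the same inpatient therapy, the arms are randomised, and the SAP plans between-group tests with a Bonferroni level for pairs. These remove the shared therapy effect, and step 5 shows that they hold their error rate. This stands in full. A reader might infer that the trial is confounded, or that it needed a run-in on therapy before the garment. The documents do not support that, since a concurrent control makes a run-in unnecessary.

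A reader might also infer that the SAP intends to credit within-arm change to the garment. It does not say so. The Protocol uses the word treatment for the two-week programme of all arms, so the SAP's wording can fairly mean change under the allocated programme. The figures above are therefore the frequency of a pattern open to misreading, not the error rate of a stated decision rule.

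Three further limits also stand:
- The documents do not say that the garment starts on the first day of therapy, that BT precedes admission, or that therapy rises at admission. They place BT before treatment and garment wear within the inpatient period.
- The repeated measures ANOVA may be meant to include group. Friedman, Wilcoxon and the paired t-test cannot.
- The immediate test of SAS and BBT looks at the garment more directly, and a paired test suits it. Its timing relative to the first therapy session is not stated.

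What the reply leaves open is the ranking. The SAP does not tie the valid between-group tests to change from BT or place them above the within-group tests.

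**Conclusion.** The point holds as a gap in the SAP, not as a flaw in the design. The within-group tests of change cannot bear on the garment, and the SAP neither says so nor specifies a between-arm analysis of change.

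With no garment effect, the pattern of a significant SPIO arm beside a non-significant control arm would arise in 17% to 38% of trials for shared standardised changes of 0.5 to 1.2, falling to 14% at 0.2 and 5% at 1.5. These figures rest on assumed effect sizes, 8 completers per arm, and a paired t-test on roughly normal change. SAS is in fact an ordinal sum from 5 to 20. The pattern is common at moderate therapy effects and nearly disappears when the therapy effect is large enough for all arms to be significant.

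The correction is worth making because it is cheap and gives the SAP a stated method for comparing change over time between arms.

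**What to change.** Change the SAP wording as follows.

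1. Base any statement about the garment on the between-arm comparison of change from BT, for SPIO 2 h v control, SPIO 6 h v control and SPIO 6 h v 2 h. A group-by-time term, or ANCOVA with the BT value as covariate, would also serve. Name one of these in advance. The planned Kruskal-Wallis and Mann-Whitney tests at 0.017 can be applied to change scores if the data are not normal.
2. Say whether the repeated measures ANOVA includes group and, if so, that the group-by-time term is the one of interest.
3. Report within-arm change from BT to PT, 1 MPT and 3 MPT as a mean or median with an interval and no p-value, described as change under the allocated programme.
4. State that significance in one arm and not in another is not evidence of a difference between them.
5. Describe the immediate with-garment test of SAS and BBT as a separate analysis, and state when it takes place relative to the first therapy session.

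The cost is the within-arm p-values, some of which would look favourable. Arms, visits, treatment and sample size do not change.

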#### **Outcome measures**

The primary outcomes of interest were feasibility and evaluating posture and balance during sitting, therefore SAS was set as the primary outcome measure while secondary outcome measures were Gross Motor Function Measure (GMFM), Box and Block Test (BBT), Parent Satisfaction Survey.

Assessments were conducted before treatment (BT) (TO), at posttreatment (PT), 1 month posttreatment (1 MPT) and 3 months posttreatment (3 MPT) (EG). SAS and BBT were also tested immediately after the orthosis was worn (EG). Children were assessed without the suit on and without any other orthosis except for the assessment of the immediate effect. During the assessment of the immediate effect children wore SPIO under their clothings to hide orthosis from the evaluator.

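### The over-time tests (Friedman, repeated-measures ANOVA) drop any child with a missed visit; a baseline-adjusted mixed model for SAS would keep the visits that were attended

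*SAP*

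**What the plan says.** The SAP (Statistical Plan) has three layers of testing.

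- **Between groups:** ANOVA, or Kruskal-Wallis if the data are not normal, then pairwise Mann-Whitney tests at 0.017 (0.05/3).
- **Within groups, in pairs of visits:** "Wilcoxon and dependent t-test will be utilized to detect within group analyzes", chosen by the distribution of the data.
- **Over time:** "To assume changes over time with treatment Friedman and repeated measures analysis of variance will be conducted".

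The SAP does not say whether the repeated-measures ANOVA carries arm as a factor, or which time points enter.

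The Protocol (Outcome measures) schedules four assessments: before treatment (BT), post-treatment (PT), and 1 and 3 months later (1 MPT, 3 MPT). SAS and the Box and Block Test are also taken once with the garment on. Under Intervention, all children are inpatients for the two treatment weeks and then continue at home, so 1 MPT and 3 MPT fall after discharge.

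Under Sample size, "8 individuals for each group must had been recruited". With three arms that is 24 children. The same section sets "a minimum clinically significant difference of 1 units of Sitting Assessment Scale score".

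Neither document states an analysis set, a missing-data method, a dropout allowance or a sensitivity analysis. Loss appears only as a retention percentage, reported for feasibility.

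**The concern.** This goes beyond missing detail, because the choice of test fixes what happens to an incomplete child. Friedman and standard repeated-measures ANOVA work on complete rows. A child seen at BT, PT and 1 MPT who misses 3 MPT contributes nothing to either, and three valid scores are discarded.

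Two things are at stake. The first is precision: with 8 children per arm, each lost row counts. The second is bias: if the children who leave differ in response from those who stay, the change shown by completers is not the change in the randomised group.

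A further limit is that Friedman has no between-arm factor. On the non-normal branch, the over-time analysis therefore gives no arm-by-time contrast at all.

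**Working it through.** **Inputs from the documents.** Three arms of 8 (24 children); four visits; minimum clinically significant difference 1 SAS point; expected means 16.47 and 13.20 with SDs 1.96 and 3.32 (Protocol, Sample size). Pooled SD = sqrt((1.96² + 3.32²)/2) = sqrt(7.432) = 2.73.

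**The plan's own figure.** For a difference of 16.47 − 13.20 = 3.27 and SD 2.73, 80% power at 5% needs 9 (normal) or 10 (t-test) per group one-sided, and 11 or 12 two-sided. A figure of 8 comes out only if the 1 point is added to the difference (4.27; two-sided t-test 7.5, rounded up). The Protocol states no allowance for loss. How 8 was reached is a separate matter and does not decide this point.

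**Step 1: rows lost.** The documents give no dropout figure. Assume each at-risk visit is missed independently with probability p. Rows dropped = 24 × (1 − (1 − p)^k), where k is the number of visits at risk.

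| Visits at risk | p = 5% | p = 10% |
|---|---|---|
| 1 MPT, 3 MPT (k = 2) | 24 × (1 − 0.9025) = 2.3 | 24 × (1 − 0.81) = 4.6 |
| PT, 1 MPT, 3 MPT (k = 3) | 24 × (1 − 0.8574) = 3.4 | 24 × (1 − 0.729) = 6.5 |

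At p = 10% this leaves 8 × 0.81 = 6.5 or 8 × 0.729 = 5.8 complete children per arm. The standard error of a within-arm mean change grows by 1/sqrt(fraction kept). That is 1/sqrt(0.9025) = 1.05 to 1/sqrt(0.81) = 1.11 with two visits at risk, and 1.08 to 1.17 with three. If the same child tends to miss both visits, fewer rows are lost at the same per-visit rate.

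**Step 2: inflation of within-arm change under selective loss.** Assume no true effect, normal scores, SD 2.73 and correlation r between any two visits. Children with no improvement at PT (half of them) leave after PT with probability q.

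- SD of change = 2.73 × sqrt(2(1 − r)).
- Mean size of change in each half: m = SD of change × sqrt(2/π), where sqrt(2/π) = 0.798.
- Fraction lost = 0.5q. Mean change in completers = 0.5q × m / (1 − 0.5q).

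For 20% loss (q = 0.4) the multiplier is 0.2/0.8 = 0.25:

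| r | SD of change | m | Inflation at PT |
|---|---|---|---|
| 0.4 | 2.99 | 2.38 | 0.60 |
| 0.7 | 2.11 | 1.68 | 0.42 |
| 0.8 | 1.72 | 1.38 | 0.34 |

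At r = 0.7, losses of 10% and 30% give 0.1/0.9 × 1.68 = 0.19 and 0.3/0.7 × 1.68 = 0.72. If one child in eight leaves (12.5%), the range over r is 0.20-0.34.

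A different pattern, with leavers drawn from the worst third on PT change, was simulated with 400,000 children per arm. At 20% loss it gave 0.47-0.81 at PT and 0.24-0.41 at 3 MPT over the same r.

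**Step 3: direction between arms.** This applies only if an arm contrast is computed on complete rows. In the worst-third simulation with 20% loss, the PT contrast was:

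- loss in the garment arm only: +0.47 to +0.81 (favours the garment);
- equal loss in both arms: about 0;
- loss in control only: −0.47 to −0.82.

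When partial rows were kept, the contrasts at PT and at 3 MPT were within 0.01 of zero in every scenario. That is expected, because leaving depended only on an observed score.

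**The case against.** The strongest objection is that the arm comparison sits elsewhere in the SAP. ANOVA or Kruskal-Wallis with Mann-Whitney pairs, run at each visit, keeps the PT score of a child who later misses 3 MPT, and a paired BT-to-PT test keeps that child too. This stands. A reader might infer that completers become the trial's analysis set and that the randomised comparison is lost; the documents do not support that. Row deletion is confined to the over-time tests.

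A reader might also infer that the garment arms are bound to be flattered. Neither document gives a dropout rate or pattern, and Step 3 shows that the direction can be either way or nil.

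Nor can it be said that all over-time tests run strictly within arms. Repeated-measures ANOVA can carry an arm factor, and the SAP is silent. Only Friedman is necessarily without one.

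The larger row losses assume that PT can be missed. Since PT closes an inpatient stay, the two-visit figures (2.3-4.6) may be nearer.

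Finally, a mixed model on a 5-20 sum score with about 8 children per arm has its own weaknesses, and a pilot that reports retention could simply state its analysis set and missing-data rule. That is a fair minimum. It would not recover the discarded visits or supply an arm-by-visit contrast when Friedman is used.

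**Conclusion.** The point holds for the over-time tests. Any child with a missed visit drops out of them, and nothing in either document provides otherwise. Loss of precision is certain once any visit is missed; its size (2.3-6.5 of 24 children) rests on an assumed 5-10% independent miss rate per visit.

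The inflation of about 0.3-0.6 SAS points concerns completers' within-arm PT change. It rests on 20% loss confined to non-improvers, SD 2.73 and correlation 0.4-0.8. The 1-point important difference gives a sense of scale, but it comes from a two-group calculation and is not a threshold for within-arm change. A between-arm bias toward the garment would need such loss to be greater in the SPIO arms than in control.

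This is a worthwhile, inexpensive improvement to the analysis. It does not invalidate the planned between-group comparison.

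**What to change.** For SAS, replace the over-time tests with one linear mixed model in SPSS:

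- arm, visit (PT, 1 MPT, 3 MPT) and arm by visit, with baseline SAS as covariate;
- all available visits of all randomised children, in their allocated arm;
- PT arm contrasts reported first;
- the in-garment immediate assessment left out. Control children wear no garment and may have no such value, so entering it as a time point in a complete-row test could remove that whole arm;
- the covariance structure and small-sample degrees-of-freedom method stated in advance.

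Keep the within-arm and rank-based tests as descriptive or supportive.

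The cost is a paragraph of SAP wording and a slightly longer analysis in software already named. The model assumes data are missing at random given the observed scores, which fails if leaving depends on something not recorded. It also assumes roughly normal residuals on a 5-20 score with about 8 children per arm. Check it against the planned rank tests and one missing-data sensitivity analysis. A child with no post-baseline SAS still contributes nothing, so report the number analysed at each visit by arm.
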